12 OCT2020

mean, median, SD and range. Dose response will be evaluated by comparing safety, and changes in efficacy variables across the dose regimens.

All individual patient data will be displayed in listings. For comparisons to baseline, data from Visit 2 prior to the first dose of study drug will be used as baseline. Subgroup analyses will be performed based on baseline groupings for FVC, region and progression-related biomarkers (CXCL13, CCL18, MMP3).

If either regimen is eliminated based on Part A outcomes, patients may be switched to the selected regimen for the remainder of their participation. Data summaries will be created to mimic this switch. Data listings will include a variable to denote the regimen switch and flag the time of the switch for affected patients.

Patients will be analyzed according to randomized treatment.

Details of data handling and summaries will be further defined in the Statistical Analysis Plan (SAP).

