4.4. Safety Endpoints

- Treatment-emergent adverse events (AEs)
- Change from pre-dose to post-dose FEV₁ after initial dose
- Treatment-emergent deaths
- Treatment-emergent changes in clinical laboratory findings
- Changes in Vital signs.

Statistical Analysis PlanSponsor: Avalyn Pharma, Inc.; Protocol No.: AP01-002

5. Analysis Sets**5.1. Safety Set**

The Safety Set (SAF) will include all randomized patients who were administered at least one dose of study medication. Patients will be analyzed according to treatment received. The SAF will be used for all analyses of safety endpoints.

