5.4. Protocol Deviations

Protocol deviations will be collected and will be categorized as:

- Informed Consent
- Enrollment Criteria
- Dosing
- Concomitant Medications
- Visits/Procedures Required
- Visit Schedule
- Non-compliance
- Regulatory
- Laboratory
- Other

They will also be graded as Major or Minor.

This document is confidential.

SAP Version: 3.0 (15JUL2021)
Controlled Document ID: **3903A.01**, Effective Date 29-Oct-2018
Filing requirements: TMF

Page 20 of 52

Statistical Analysis PlanSponsor: Avalyn Pharma, Inc.; Protocol No.: AP01-002

Major protocol deviations are defined as a subset of protocol deviations that may significantly impact the completeness, accuracy, and/or reliability of the study data or that may significantly affect the subject's rights, safety or well-being. Major protocol deviations will be included in the Clinical Study Report (CSR). These include: Enrollment Criteria (violation of inclusion/exclusion criteria, Informed Consent (informed consent not provided), Dosing (study drug deviation), Non-compliance, Concomitant Medications (administration of prohibit medication) and Other Good Clinical Practice (GCP) deviations. All protocol deviations will be tracked and corrective live actions implemented.

Protocol deviations will be summarized by grade and category for each treatment group and overall in the following ways:

- Patients with Any Protocol Deviations (Major or Minor)
- Patients with Major Deviations Only
- Patients with Minor Deviations Only (i.e. excluding those patients with Major deviations).
- Protocol Deviations Attributable to COVID-19

All protocol deviations will be listed.

This document is confidential.

SAP Version: 3.0 (15JUL2021)
Controlled Document ID: **3903A.01**, Effective Date 29-Oct-2018
Filing requirements: TMF

Page 21 of 52

Statistical Analysis PlanSponsor: Avalyn Pharma, Inc.; Protocol No.: AP01-002

6. General Aspects for Statistical Analysis**6.1. General Methods**

Unless otherwise specified, all data will be summarized by treatment group and overall. A separate summary of data from Part A of will be provided in addition to a full study summary including both Part A and Part B data. Categorical data will be summarized as number and percent of total. Continuous data will be summarized using mean, median, SD and range. Dose response will be evaluated by comparing safety and changes in efficacy variables across the dose regimens.

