All relevant patient data will be included in listings. All patients entered into the database will be included in patient data listings.

Pulmonary function tests (PFTs) (including D_{LCO}) are performed at each study visit.

The following PFTs will be performed at all visits (including Screening) using spirometry (and documented on the PFT eCRF form):

- FVC Liters (L)
- FEV₁ Liters (L)
- % Predicated FVC
- % Predicted FEV₁.

Pre-dose and post-dose spirometry will be performed at the Baseline visit.

At every visit, D_{LCO} ($\text{mL}/\text{min}^{-1}/\text{mmHg}^{-1}$) and % Predicted D_{LCO} will be obtained using the site's standard methodology.

FEV₁/FVC ratio will be derived as: $100 \times \text{FEV}_1/\text{FVC}$.

For comparisons to baseline, data from Visit 2 prior to the first dose of study drug will be used as baseline, unless otherwise noted. For PFTs, the pre-dose result will be used as baseline. Subgroup analyses will be performed based on baseline groupings for FVC, region, age, sex, D_{LCO} and progression-related biomarkers (CXCL13, CCL18, MMP3).

If either regimen is eliminated based on Part A outcomes, patients may be switched to the selected regimen for the remainder of their participation. Data summaries will be created to mimic this switch by using the following treatment grouping for Part B: (1) randomized to 100 mg twice daily; (2) randomized to 50 mg once daily and stayed on 50 mg once daily; (3) randomized to 50 mg once daily and switched to 100 mg twice daily; (4) randomized to 50 mg once daily total [groups 2 and 3 combined]; (5) overall total for Part B data. Descriptive within-patient analyses will be included for those patients who switch from 50 mg once daily to 100 mg twice daily. These analyses will include spider plots of change from baseline showing when the dose switch took place. Data listings will include a variable to denote the regimen switch and flag the time of the switch for affected patients.

No formal hypothesis tests are planned.

This document is confidential.

SAP Version: 3.0 (15JUL2021)
Controlled Document ID: **3903A.01**, Effective Date 29-Oct-2018
Filing requirements: TMF

Page 22 of 52

Statistical Analysis PlanSponsor: Avalyn Pharma, Inc.; Protocol No.: AP01-002

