6.6. Subgroups

Subgroup analyses will be performed based on baseline groupings for FVC % predicted (FVC % predicted \leq 65, 65 < FVC % predicted < 80, and FVC % predicted \geq 80 at Baseline), region (Asia-Pacific and Europe), supplemental oxygen use (Y/N), age at screening categorized as >Median level vs. \leq Median level, sex, DLCO % predicted categorized as >Median level vs. \leq Median level, and progression-related biomarkers (CXCL13, CCL18, MMP3) each categorized as >Median level vs. \leq Median level provided each stratum contains at least 10 patients. Analyses of the primary efficacy endpoint will be performed by each subgroup in addition to by treatment group. In addition, a general

This document is confidential.

SAP Version: 3.0 (15JUL2021)
Controlled Document ID: **3903A.01**, Effective Date 29-Oct-2018
Filing requirements: TMF

Page 24 of 52

Statistical Analysis PlanSponsor: Avalyn Pharma, Inc.; Protocol No.: AP01-002

safety summary (overall AE summary, summary of respiratory [SOC respiratory, thoracic and mediastinal disorders] TEAEs by Preferred Term and summary of tolerability including cough due to drug administration and bronchospasm after in-clinic drug administration) will be performed by each subgroup in addition to by treatment group.

This document is confidential.

SAP Version: 3.0 (15JUL2021)
Controlled Document ID: **3903A.01**, Effective Date 29-Oct-2018
Filing requirements: TMF

Page 25 of 52

Statistical Analysis PlanSponsor: Avalyn Pharma, Inc.; Protocol No.: AP01-002

7. Demographic, Other Baseline Characteristics and Medication**7.1. Patient Disposition and Withdrawals**

The number of patients in each study population will be summarized by treatment group and overall. In addition, for each study part (Part A and Part B), patients' status with regard to study treatment and follow-up will also be summarized by treatment group and overall, along with the reasons for study discontinuations. The timing of the switch to 100 mg twice daily in Part B for 50 mg once daily patients and duration of time on 100 mg twice daily will be summarized.

All patient disposition data will be presented in a listing.

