The population used for safety analyses will be the SAF. Safety will be assessed on the basis of AE or adverse drug reactions (ADR) reports, clinical laboratory data, ECG parameters, physical examinations, vital signs and change from pre-dose to post-dose FEV₁ after initial dose.

Treatment-emergent AEs (any AEs recorded during or following the first study drug administration) will be summarized by treatment group and categorized by severity and relationship to the study procedures and to the investigational product (IP). If a patient has more than 1 occurrence of the same AE, he/she will be counted only once within that preferred term in the summary tables. The most severe occurrence of an AE, as well as the most extreme relationship of the AE to the study procedures and IP, will be indicated in cases of multiple occurrences of the same AE. SAEs will be summarized separately.

All AE data will be presented in a listing. Additionally, listings of SAEs and AEs leading to discontinuation will be generated. All SAEs will be evaluated to determine whether they are SUSARs or Unexpected Adverse Device Effects.

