10.1. Adverse Events / Adverse Drug Reactions

An adverse event (AE) is any untoward medical condition that occurs in a patient while participating in this clinical study. Adverse events will be coded according to the Medical Dictionary for Regulatory Activities (MedDRA 21.1 or higher) terminology and the severity of the toxicities will be graded according to the National Cancer Institute (NCI) Common Terminology Criteria for Adverse Events (CTCAE), v5.0, where applicable. An adverse drug reaction (ADR) means any AE caused by a drug or biologic.

Treatment-Emergent Adverse Events (TEAEs) are those adverse events/adverse drug reactions that are recorded during or following the initiation of AP01 medication administration, and do not necessarily have a causal relationship to the use of the study medication. Treatment-Emergent Adverse Events (simply referred to as adverse events in summary tables) will be summarized.

The following adverse event summary tables will be summarized by treatment group and combined over both treatment groups:

- 1) An overall summary with the number and percentage of patients reporting AEs, serious AEs, grade 3 or higher AEs, treatment-related AEs, AEs leading to study treatment (AP01) discontinuation and AEs with outcome of deaths. In addition, this overall summary will be performed for each subgroup listed in Section 6.6.
- 2) AEs overall and by system organ class and preferred term. In this summary, a patient is counted once at the system organ class and once at each preferred term within the system organ class. In addition, this summary will be performed for each subgroup listed in Section 6.6.
- 3) A separate summary of respiratory [SOC respiratory, thoracic and mediastinal disorders] TEAEs by Preferred Term and summary of tolerability including cough due to drug administration and bronchospasm after in-clinic drug administration) will be performed by each subgroup listed in Section 6.6.

This document is confidential.

Statistical Analysis PlanSponsor: Avalyn Pharma, Inc.; Protocol No.: AP01-002

- 4) AEs overall and by system organ class, preferred term and highest CTCAE grade.

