In this summary, a patient is counted once at the highest grade for which the event occurred in the system organ class and the highest grade for each unique preferred term within that system organ class. Therefore, patients may only contribute once to each preferred term and once to each system organ class. The missing severity grade will be reported in a separate category.

- 5) Study-treatment-related AEs overall and by system organ class and preferred term.

All those AEs with relationship to AP01 marked as “Possibly Related” or “Probably Related” or missing will be reported in the table.

- 6) Study-treatment related AEs by system organ class, preferred term and Highest CTCAE grade
- 7) AEs leading to study treatment termination by system organ class and preferred term
- 8) AEs leading to study treatment termination by system organ class, preferred term and highest CTCAE grade
- 9) CTCAE Grade 3 or higher AEs, overall and by system organ class and preferred term

A Serious Adverse Event (SAE) is an AE that falls into one or more of the following categories:

- a. Results in death
- b. Is life-threatening
- c. Requires inpatient hospitalization or prolongation of existing hospitalization
- d. Results in persistent or significant disability or incapacity
- e. Is a congenital anomaly/birth defect
- f. Is any other important medical event

Serious adverse events will be summarized by treatment group and combined over both treatment groups.

- 1) SAEs overall and by system organ class and preferred term.

In this summary, a patient is counted once at the system organ class and once at each preferred term within the system organ class.

- 2) SAEs overall and by system organ class, preferred term and highest CTCAE grade.

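### SAP 10.1 has no rule assigning adverse events to the regimen at onset, so the full-study AE and SAE tables mix 50 mg and 100 mg events for patients converted to 100 mg twice daily

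*SAP*

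**What the plan says.** The protocol synopsis (Study Overview/Design) records the data monitoring board's recommendation of 12 October 2020. Everyone treated in Part B after the amendment receives 100 mg twice daily, and patients already in Part B on 50 mg once daily are converted. Protocol 11.2 says summaries will reflect such a switch and listings will flag it. It then states "Patients will be analyzed according to randomized treatment" and leaves the details to the SAP.

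The SAP responds in several places:

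- SAP 6.1 plans a Part A summary "in addition to a full study summary including both Part A and Part B data". For Part B it sets five groupings, one of which is "3) randomized to 50 mg once daily and switched to 100 mg twice daily". It also promises descriptive within-patient analyses for converted patients, naming spider plots of change from baseline.
- SAP 6.2.8 defines a Dosing Switch Date.
- SAP 7.1 says the timing of the switch and the "duration of time on 100 mg twice daily will be summarized".
- SAP 7.5 calculates compliance by regimen for converted patients.
- SAP 8.1, 8.2.6 and 9.4 let treatment vary over time in longitudinal models. SAP 8.1 and 9.2 drop post-switch data from the slope and home-spirometry analyses.

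For adverse events, SAP 5.1 says of the Safety Set: "Patients will be analyzed according to treatment received". SAP 10.1 says "The following adverse event summary tables will be summarized by treatment group and combined over both treatment groups", with the same layout for SAEs, and ties treatment emergence only to the start of AP01. SAP 10 adds that a patient with repeated occurrences of one AE is such that "he/she will be counted only once within that preferred term in the summary tables".

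**The concern.** Safety and tolerability are the primary objective (SAP 3.1). Comparing the safety of the two regimens to guide later studies is a listed objective (SAP 3.2), and Part B exists to collect long-term data. A converted patient contributes events from both regimens. Without a rule based on onset, a 72-week AE table cannot show which regimen the patient was on when an event began. If those patients are counted under 50 mg, events that began on 100 mg are credited to the lower dose and the two columns are drawn together. If they sit in a column of their own, that column is a blend. Either way, someone interested in the longer-term tolerability of 100 mg twice daily would have to rebuild the counts from flagged listings.

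**Working it through.** The plan's only AE figure is the chance of seeing at least one event among 50 patients, 1 − (1 − p)^50. At p = 1%, 5% and 10% this gives 0.395, 0.923 and 0.995, matching SAP Table 1. The figure is correct and does not bear on this point, which is a matter of reading the text.

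**1. Does any rule place an event by regimen?**

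| Provision | What it classifies | Resolves a converted patient's AEs? |
|---|---|---|
| Protocol 11.2, randomised treatment | patient | No: later 100 mg events stay under 50 mg |
| SAP 5.1, treatment received | patient | No: undefined for someone who received both |
| SAP 6.1, Part B groupings | patient | Partly: separates converted patients, not their events, and for Part B only |
| SAP 6.2.8, Dosing Switch Date | date | Could, but no AE rule refers to it |
| SAP 10.1, treatment emergence | event | No: anchored to first AP01 dose only |

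SAP section 12 lists only the added Full Analysis Set as a change from the protocol, so it does not reconcile the first two rows.

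**2. Where does mixing occur?**

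- *Full-study tables (Parts A and B):* for every converted patient, because all of them spent Part A on 50 mg.
- *Part B tables, switched column:* for patients converted after entering Part B. Those converted at entry are unmixed there.
- *Part B columns for patients randomised to 100 mg and for those who stayed on 50 mg:* no mixing from conversion.
- *Part A tables:* none, because conversion happens only in Part B.

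**3. How many tables are open to it?** SAP 10.1 lists AE items 1–9 and SAE items 1–2: 9 + 2 = 11. All 11 can mix by onset. That includes "AEs leading to study treatment termination by system organ class and preferred term": a converted patient's discontinuation must follow the switch, but the AE that caused it may have begun before. The same holds for AEs with a fatal outcome.

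**4. Counting once.** A term reported at 50 mg that recurs after the switch at the same or a lower grade adds nothing to the table, so the recurrence is invisible.

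**5. How much follow-up is involved?** The documents give neither the number nor the timing of conversions. The visit schedule gives only the shares for a switch on day d, assuming follow-up to Day 504. The share at 50 mg is d/504 of the full study and (d − 168)/336 of Part B.

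| Switch at | Full study at 50 mg | Part B at 50 mg |
|---|---|---|
| Week 24 (d = 168) | 33.3% | 0% |
| Week 36 (d = 252) | 50.0% | 25% |
| Week 48 (d = 336) | 66.7% | 50% |
| Week 60 (d = 420) | 83.3% | 75% |

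**6. Illustration of dilution.** Assume constant event rates, every 50 mg patient converted in the same week s, 72 weeks of follow-up, and counting by randomised arm. With a true 100 mg to 50 mg rate ratio R, the apparent ratio is R ÷ [(s + (72 − s)R)/72].

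- R = 2, s = 24: 2 ÷ (120/72) = 1.20.
- R = 2, s = 60: 2 ÷ (84/72) = 1.71.
- R = 1.5: 1.13 (s = 24) to 1.39 (s = 60).
- R = 3: 1.29 to 2.25.

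These values of R and s are assumed. They show the direction of the effect and are not an estimate for this trial, whose tables count patients rather than rates.

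**The case against.** The best defence is that the plan does deal with the switch. The protocol's sentence on randomised treatment follows a commitment to reflect the switch in summaries, and it defers to a SAP that sets the Part B groupings, defines the switch date and flags it in listings. A reader might infer from that one sentence that the protocol simply files all converted patients' 100 mg events under 50 mg. In context the documents do not say so. The combined 50 mg grouping in SAP 6.1 is also openly labelled as randomised, and the within-patient analyses are not limited to the spider plots named. All of this stands, but none of it supplies a rule for events or a switched column for the full-study tables.

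A second defence is that little turns on it. The regimen comparison comes from Part A, and Protocol 1.2.4 says preliminary six-month results had already let the board choose 100 mg twice daily. No formal hypothesis tests are planned for these tables. This also stands. A reader might infer that the dose choice was compromised; the documents do not support that.

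Third, a date split is not a split by actual dose. Protocol 8.7 recommends stepping down to 50 mg twice daily, then once daily, for intolerance, and the Dosing Switch Date records only the upward change. That is right, and it governs how the periods should be labelled.

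Fourth, SAP Table 6 imputes partial AE dates only to decide treatment emergence, so it causes no bias in the plan as it stands. Reusing it to assign period would: a missing day becomes the first of the month, which usually falls before a switch in that month. Counting all such events as post-switch would err the other way.

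**Conclusion.** The point holds. Followed as written, SAP 10.1 mixes events from the two regimens in the full-study AE and SAE tables for every converted patient, and in the Part B switched column for patients converted during Part B. This weakens the long-term description of safety by regimen, on the trial's primary objective. It leaves the 24-week Part A comparison intact.

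The size cannot be computed, because conversions are neither counted nor dated in the documents. The ceiling is the roughly 50 patients randomised to 50 mg. The follow-up shares above depend on an unknown switch week, and the dilution figures on assumed rates. Two stronger readings go too far: that the SAP overlooks the switch, which it handles explicitly for compliance, FVC and DLCO; and that a known amount of dilution has been shown. This is an inexpensive improvement that should be made. It does not invalidate the safety analysis.

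**What to change.** In SAP 10.1:

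1. State that the Part B grouping of SAP 6.1 applies to the AE and SAE tables.
2. Assign each treatment-emergent AE to before or after the Dosing Switch Date (SAP 6.2.8) by its onset date.
3. Add one descriptive table for converted patients showing treatment-emergent AEs and SAEs, including respiratory events and cough, before and after conversion. Count each patient once per term per period and show patient-time in each period.
4. Label the periods as before and after conversion, not by actual dose, because step-down is allowed.
5. Report separately any event whose missing or partial onset date cannot be placed on either side of the switch.

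The cost is one extra table. Onset dates are collected (Protocol 10.1.4.3.1), the switch date is defined, and time on 100 mg is already to be summarised (SAP 7.1). The before/after contrast is confounded by disease progression and by nintedanib, which is permitted in Part B. An onset date will also not show an event that began at 50 mg and worsened at 100 mg. The table should therefore be read as description only.
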